3.1.6 Additional Justification of Sample Size Parameters

The PG of 6-month ORR for Tandem was based on the primary endpoint results (6-month tumor response by EASL) in the PRECISION V (Lammer et. al. 2010), a phase II RCT, published by CardioVascular and Interventional Radiology (Springer).

[figure not shown]

Fig. 2 Tumor response at 6 months (LOCF) (MITT population and advanced patient group* ***). * More advanced disease was at least one of Child-Pugh B, ECOG 1, undergone prior curative treatment (i.e., recurrent disease), and presence of bilobar disease. In accordance with the EASL criteria: complete response (CR)—complete disappearance of all known viable tumor (assessed via uptake of contrast in the arterial phase of the MRI scan) and no new lesions; partial response (PR)—50% reduction in viable tumor area of all

measurable lesions; stable disease (SD)—all other cases; progressive disease (PD)—25% increase in size of one or more measurable lesions or the appearance of new lesions. Objective response (OR) was defined as CR + PR, and disease control (DC) as CR + PR + SD. ** Analysis of advanced patient subgroup: OR rate, P=0.038; DC rate, P=0.026; CR rate, P=0.091 (chi-square analysis)

The 6-month ORRs were reported as 51.6% (48/93) vs. 43.5% (47/108) for DC Bead and cTACE respectively. The 95% exact confidence intervals were estimated by SAS: 51.6% with 95% CI: 41.0%, 62.1% and 43.5% with 95% CI: 34.0%, 53.4% for DC Bead and cTACE

respectively. Therefore in order to demonstrate the significant treatment effect over the cTACE, the PG of 45% based on the performance of cTACE was chosen.

3.2 Primary Safety Endpoint

The primary safety hypotheses are not specified. However the safety endpoints are pre-specified in the Safety Plan and will be monitored against the reference rates on a regular basis.

The safety endpoints to be observed in 6 weeks post treatment initiation are:

- All-cause death
- Liver failure
- Hepatic abscess

3.3 Success Criteria

The study success is based on the PG assessment for the primary effectiveness endpoint in at least the minimum of 6-month evaluable subjects. The Tandem will be concluded as meeting the endpoint for device effectiveness if the one-sided lower 97.5% confidence bound of the observed 6-month ORR is greater than zero.

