10.3. Enrollment Control

A minimum of 98 enrolled subjects are needed to adequately assess the primary endpoint at 6 months after initial treatment. To account for attrition, minimum enrolment shall be 109 subjects, assuming a maximum attrition of 10% for all reasons at 6 months. The enrollment cap for each study site is 25% of total enrolled subjects, which is 27 subjects. The study recruitment will stop when 109 qualified subjects completed enrollment.

11. Study Methods

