12.1.1.2. Sample Size

The overall sample size is driven by the primary effectiveness endpoint. Approximately 109 subjects are planned to be enrolled in the study. The sample size justification is based on the following assumptions.

- Power $\geq 85\%$
- One-sided significance level = 2.5% (alpha)
- PG for 6-month ORR = 45%
- Expected 6-month ORR = 60%
- A minimum of 98 evaluable subjects are required for 6-month assessment
- Attrition rate = 10% (loss to follow-up in 6 months)
- A sample size of 109 subjects will be enrolled in the study

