The null hypothesis (H_0) states that the PG is not met as opposed to the alternative hypothesis (H_1) which states that the PG is met. The hypotheses inequalities are shown below:

 H_0 : $Pt \le PG$ (not met)

 H_1 : Pt > PG (met)

where Pt is the 6-month ORR for the subjects treated with Tandem and the PG is 45%. The PG development is based on the PRECISION V, an international multicenter phase II randomized clinical trial (RCT).

3.1.3 Effectiveness Sample Size

The overall sample size is driven by the primary effectiveness endpoint. Approximately 109 subjects are planned to be enrolled in the single-arm study. The sample size justification is based on the following assumptions.

- Power > 85%
- One-sided significance level (alpha) = 2.5%
- PG for 6-month ORR = 45%

- Expected 6-month ORR = 60%
- A minimum of 98 evaluable subjects to be required at 6 months
- Attrition rate in 6 months $\leq 10\%$
- A maximum of 109 subjects to be enrolled in the study at baseline

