3.1.4 Effectiveness Statistical Methods

A normal approximation test (e.g. Chi-Square Test) for comparing the observed 6-month ORR with the PG will be used to assess the effectiveness hypotheses for a minimum of 98 evaluable subjects.

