3.1.5 Worst Case Assessment for Effectiveness

The worst case below reflects the analysis for 98 evaluable subjects. If the actual attrition is better than expected, the worst case scenario will be reassessed.

The PG of 45% will require a minimum of 52 responders at 6 months out of 98 evaluable subjects treated with Tandem. That is, the observed 6-month ORR in Tandem will need to be at least 53.1% (52/98) in order to claim the study effectiveness.

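### SAP 3.3 ties study success to a minimum of 98 evaluable subjects, with recruitment stopping at 109 and no rule for what happens below 98; the other success statements carry no such floor

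*SAP*

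**What the plan says.** The floor appears in three places in the SAP.

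- SAP 3.1.3, among the sample-size assumptions: "A minimum of 98 evaluable subjects to be required at 6 months".
- SAP 3.1.4, inside the specification of the test, which "will be used to assess the effectiveness hypotheses for a minimum of 98 evaluable subjects".
- SAP 3.3, where success rests on the comparison with the goal "in at least the minimum of 6-month evaluable subjects".

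Enrolment is bounded above. SAP 3.1.3 has "A maximum of 109 subjects to be enrolled in the study at baseline", and Protocol 10.3 has "The study recruitment will stop when 109 qualified subjects completed enrollment". Protocol 10.3 also calls 109 the minimum enrolment, and both sample-size sections say approximately 109.

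Attrition is described in different ways. Protocol 10.3 sizes the trial "assuming a maximum attrition of 10% for all reasons at 6 months". SAP 3.1.3 also gives 10% as an upper limit. Protocol 12.1.1.2 and both synopses set it equal to 10% and label it loss to follow-up.

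SAP 3.1.1 excludes from the primary analysis any subject without a 6-month tumour assessment. The only provision for a different number of evaluable subjects is in SAP 3.1.5: "If the actual attrition is better than expected, the worst case scenario will be reassessed". Nothing covers attrition that is worse than expected.

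The success rules in Protocol 12.1.1.4 and in the protocol and SAP synopses ask only that the one-sided 97.5% lower bound exceed the goal. They set no minimum number of subjects.

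**The concern.** A sample-size target says how many subjects the design needs for its power. A condition in the success section says when a conclusion may be drawn. SAP 3.3 and 3.1.4 place the target where a condition belongs and do not say which is meant. If it is a condition, a trial with 97 evaluable subjects and a clearly positive response rate has no stated conclusion under SAP 3.3, yet succeeds under Protocol 12.1.1.4. This is an open single-arm trial with one hypothesis test, so the question should be settled before the evaluable count and the responses are known.

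The margin is thin. Eleven losses leave exactly 98 and a twelfth leaves 97. Under SAP 3.1.1 a death, a withdrawal or a missed scan before month 6 each appears to draw on the same allowance.

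**Working it through.** **Inputs.** Goal 45%, expected response rate 60%, one-sided alpha 2.5%, power 85%, 98 evaluable, 109 enrolled, 10% attrition (SAP 3.1.3; Protocol 12.1.1.2).

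**1. The plan's own figures reproduce.** With the null variance for alpha and the alternative variance for power:

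n = ((1.960·√(0.45·0.55) + 1.036·√(0.60·0.40)) / 0.15)² = 97.7, rounded up to 98.

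Enrolment: 98/0.90 = 108.9, rounded up to 109. Expected evaluable at 10% loss: 109 × 0.90 = 98.1. So 109 reaches the floor on average, with almost nothing to spare.

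**2. Chance of falling below 98.** Assume each of 109 subjects is non-evaluable independently with probability a. Then P(fewer than 98) = P(at least 12 lost) = 1 − BinomCDF(11; 109, a).

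| Loss probability a | P(fewer than 98 evaluable) |
|---|---|
| 5% | 0.8% |
| 8% | 16.2% |
| 9% | 27.5% |
| 10% | 40.8% |
| 12% | 66.8% |
| 15% | 90.8% |

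Only 10% comes from the documents; the other rates are assumed, to show the range. If instead 10% is a ceiling on the realised proportion, at most 10 subjects are lost (0.10 × 109 = 10.9), at least 99 remain, and the floor is always met.

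**3. Effect on the probability of success at a true rate of 60%.** Let K be the number evaluable and c(k) the smallest responder count out of k that passes the normal-approximation test against 45%. Success probability = Σ P(K = k) · P(X ≥ c(k) | k, 0.60), summed over all k without a gate and over k ≥ 98 with one. At a = 10%:

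- without the gate: 85.1%
- with the gate: 50.9%

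**4. Does the test still work below 98?** The first passing count is the same by the Wald lower bound and by the score test. Power is exact binomial at 60%.

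| Evaluable | First passing count | Power |
|---|---|---|
| 90 | 50 | 83.4% |
| 95 | 53 | 82.7% |
| 97 | 54 | 83.5% |
| 98 | 54 | 86.3% |

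Exact power moves in a saw-tooth because counts are whole numbers. Over every number from 90 to 97 it lies between 81.0% (at 91) and 85.6% (at 96). Losing a few subjects below 98 therefore costs a few points of power and does not invalidate the test.

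**The case against.** The strongest case is that there is no gate. In SAP 3.3 only the first, descriptive sentence mentions the minimum; the sentence that states when effectiveness is concluded has no condition on numbers, and neither do Protocol 12.1.1.4 or the two synopses. On that reading 98 is a planning figure throughout and success is reachable at 97. This is a fair reading. A reader might infer from SAP 3.3 that the trial has about a 41% chance of ending with a success rule that no result can satisfy. The documents do not establish that. It needs the gate reading, and it needs 10% to be an average independent risk, where two sections word it as a ceiling. What stands is that the SAP supports both readings and does not choose. A planning ceiling also does not control what happens, and no section says what follows if it is exceeded.

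Other points on that side:

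- **No replacement** is an inference from the recruitment stop and from silence. It is not stated.
- **Who counts as missing is itself unclear.** Protocol 12.1.1 treats as missing a subject with no tumour assessment after treatment starts, which is narrower than SAP 3.1.1. On the protocol's wording fewer subjects would use up the allowance.
- **A forced post-hoc rule change** might also be inferred. It does not follow: SAP 5.12 and Protocol 12.3.6 allow a documented amendment before the primary analysis, and the evaluable count can be established before the response rate is tested.
- **A floor has some purpose.** With missing subjects excluded, it limits how much data can be dropped before success is claimed. This has force, but the worst-case and tipping-point analyses in SAP 5.5 address that risk directly, and a cut at 98 does so only crudely.

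**Conclusion.** The concern holds as an ambiguous success condition that conflicts with the other statements of the success rule and has no provision below 98. It is a should-fix matter of wording. It does not show that the design is unsound: 98 and 109 are correctly derived.

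If the clause is read as a gate and loss is an independent 10% per subject, the chance of falling short is 40.8% and the probability of success at a 60% response rate drops from about 85% to about 51%. Both figures are conditional on those assumptions. The shortfall risk ranges from 16.2% at 8% loss to 66.8% at 12%, and it is zero if realised attrition stays within the stated ceiling.

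**What to change.** - In SAP 3.3 and 3.1.4, remove the minimum as a condition of the test. State that the single test against the 45% goal is run on all subjects in the primary analysis set, whatever their number, and that 98 is the planning figure for 85% power.
- In SAP 3.1.5, state that the responder threshold is recomputed for the actual number evaluable in either direction.
- Report the SAP 5.5 worst-case and tipping-point analyses alongside the primary result, so that a shortfall is judged by its effect on the conclusion.
- Define attrition as all reasons in every section, replacing the loss-to-follow-up label in Protocol 12.1.1.2 and both synopses.
- In the same revision, reconcile the comparison of the lower bound with zero in SAP 3.3 with the comparison with the goal in Protocol 12.1.1.4 and both synopses. That is a separate and more serious error in the same section.

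The cost is text only. If fewer than 98 are evaluable, power is slightly below plan, about 83% at 90 to 97. If the sponsor does want a gate, the SAP should say so, state the consequence of missing it, and size enrolment for it: on the same 10% assumption the chance of fewer than 98 evaluable is 9.8% with 113 enrolled and 3.7% with 115. That route adds subjects; the wording change does not.

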Exclusion Criteria	 Subjects will be excluded for the following reasons: Presence of vascular invasion or extra-hepatic spread of disease, or diffuse HCC, defined as >50% liver involvement, or arteriovenuous fistula Macrovascular invasion of main or primary branches of portal vein at entry into the study Any contraindication for TACE treatment Any contraindication for Epirubicin administration Advanced liver disease (bilirubin levels >2 mg/dl, AST 		
	or ALT >5 times upper limit of normal) 6. Renal failure or insufficient renal function (Creatinine levels >2 mg/dl)		
	7. Subject unable to receive MRI examination		
	8. Pregnant or breast feeding woman, or plan to become pregnant during treatment or within 12 months of treatment		
	9. couldn't commit reliable birth control measures during treatment or within 12 months of treatment		
	10. Subject is participating other investigational drug or device clinical trial within 30 days of signing the informed consent		
	11. Subject is not suitable to participate in the study as judged by investigator		
Statistical Methods			
Primary Study Hypotheses	The primary hypothesis is that the 6-month ORR in the Tandem microspheres embolization and drug delivery arm is higher than the performance goal (PG).		
	The null (H_0) and alternative (H_1) hypotheses for this primary endpoint are presented below.		
	$H_0: P_e \leqslant PG$		
	$H_1: P_e > PG$		
	where P _e is the expected 6-month ORR (%).		
Statistical Test	A normal approximation test will be used to assess the one-sided hypotheses of the test device superior to the PG		

Form/Template 90702637 Rev/Ver AH STOPPER China Protocol, 92040370 Rev/Ver AD Page 10 of 59

Success Criteria for the PG	The test device will be concluded to be superior to the PG in the primary analysis if the one-sided lower 97.5% confidence bound for the test device performance in 6-month ORR is greater than PG.
Sample Size Parameters	The overall sample size (N=109) is driven by the primary effectiveness endpoint. • Power ≥ 85% • One-sided significance level = 2.5% (alpha) • PG for 6-month ORR = 45% • Expected 6-month ORR = 60% • Total N=98 subjects are required for 6-month assessment • Attrition rate = 10% (loss to follow-up in 6 months) • Approximately N=109 subjects to enroll

Form/Template 90702637 Rev/Ver AH STOPPER China Protocol, 92040370 Rev/Ver AD Page 11 of 59

3. Table of Contents

1.	Title Page	1
2.	PROTOCOL SYNOPSIS	6
3.	TABLE OF CONTENTS	11
4.	Introduction	16
5.	DEVICE DESCRIPTION	17

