12.1.1.4. Success Criteria

The test device will be concluded to be superior to the PG if the one-sided 97.5% lower confidence bound for the observed performance in 6-month ORR is greater than PG.

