	 5. Advanced liver disease (bilirubin levels >2 mg/dl, AST or ALT >5 times upper limit of normal) 6. Renal failure or insufficient renal function 	
	7. Subject unable to receive MRI examination	
	8. Pregnant or breast feeding woman, or plan to become pregnant during treatment or within 12 months of treatment	
	9. Couldn't commit reliable birth control measures during treatment or within 12 months of treatment.	
	10. Subject is participating other investigational drug or device clinical trial within 30 days of signing the informed consent.	
	11. Subject is not suitable to participate in the study as judged by investigator	
Statistical Methods		
Primary Study Hypotheses	The primary hypothesis is that the 6-month ORR in the Tandem microspheres embolization and drug delivery arm is higher than the performance goal (PG).	
	The null (H ₀) and alternative (H ₁) hypotheses for this primary endpoint are presented below.	
	H_0 : $P_e \leqslant PG$	
	$H_1: P_e > PG$	
	where P _e is the expected 6-month ORR (%).	
Statistical Test	A normal approximation test will be used to assess the one-sided hypotheses of the test device superior to the PG	

Success Criteria for the PG	The test device will be concluded to be superior to the PG in the primary analysis if the one-sided lower 97.5% confidence bound for the test device performance in 6-month ORR is greater than PG.
Sample Size Parameters	The overall sample size (N=109) is driven by the primary effectiveness endpoint. • Power ≥ 85% • One-sided significance level = 2.5% (alpha) • PG for 6-month ORR = 45% • Expected 6-month ORR = 60% • Total N=98 subjects are required for 6-month assessment • Attrition rate = 10% (loss to follow-up in 6 months) • Approximately N=109 subjects to enroll

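### SAP 3.3 sets the success threshold for the 6-month ORR at zero instead of the 45% performance goal

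*SAP*

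**What the plan says.** SAP 3.3 (Success Criteria) has two sentences. The first ties success to the performance goal: "The study success is based on the PG assessment for the primary effectiveness endpoint". The second gives the operative rule and compares the bound with a different number. Tandem meets the endpoint "if the one-sided lower 97.5% confidence bound of the observed 6-month ORR is greater than zero".

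The other statements of the success rule use the PG:

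- Protocol 12.1.1.4 requires that the "one-sided 97.5% lower confidence bound for the observed performance in 6-month ORR is greater than PG".
- The protocol synopsis requires that the "confidence bound for the test device performance in 6-month ORR is greater than PG".
- The SAP's own synopsis requires that the "one-sided lower 97.5% confidence bound for the test device performance in 6-month ORR is greater than PG".

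The surrounding sections of the SAP agree with these. Section 3.1.2 sets H0: Pt ≤ PG, "where Pt is the 6-month ORR for the subjects treated with Tandem and the PG is 45" per cent. Section 3.1.3 gives "One-sided significance level (alpha) = 2.5" per cent. Section 3.1.4 plans a normal-approximation test of the observed ORR against the PG, and the SAS code in section 7.2 uses a null proportion of 0.45.

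**The concern.** The second sentence of SAP 3.3 places the bound on the observed ORR, not on the ORR minus the PG. A lower bound above zero shows only that some subjects respond. It says nothing about H0: Pt ≤ 45%, so the rule as written does not test the stated hypothesis and cannot be reconciled with the protocol.

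SAP section 2 bases study success on a single set of hypotheses, and section 3.3 is where the decision rule for them is stated. If that rule were applied literally, the trial's one confirmatory decision would have no type I error control against the PG. Programming, analysis and validation are assigned to an independent CRO (SAP 5.11, 6 and 7), which would be working from an SAP with two incompatible success rules.

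**Working it through.** **Inputs.** PG p0 = 0.45 (SAP 3.1.2). Expected ORR p1 = 0.60, one-sided alpha 0.025, power 85%, 98 evaluable subjects and 10% attrition (SAP 3.1.3, Protocol 12.1.1.2). Normal-approximation test (SAP 3.1.4). z(0.975) = 1.960 and z(0.85) = 1.036.

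**Step 1: which null was the trial sized against?**

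n = [(z(0.975)·√(p0(1−p0)) + z(0.85)·√(p1(1−p1))) / (p1−p0)]²
= [(1.960 × 0.4975 + 1.036 × 0.4899) / 0.15]²
= 97.7, rounded up to 98.

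Inflating for attrition, 98/0.9 = 108.9, or 109. Power at n = 98 is 85.1%. The plan's figures reproduce with a null of 45%.

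**Step 2: the rule as written in SAP 3.3, n = 98.** The Wald lower bound is L(x) = p − 1.960·√(p(1−p)/98), with p = x/98.

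- x = 3: p = 0.0306, L = −0.0035, not above zero.
- x = 4: p = 0.0408, L = 0.0408 − 1.960 × 0.0200 = +0.0016, above zero.

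Success therefore starts at 4 of 98. With the Wilson or Clopper-Pearson bound it starts at 1 of 98.

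The probability of declaring success is P(X ≥ cut-off) for X ~ Binomial(98, true ORR):

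| True ORR | Rule as written, Wald (≥ 4/98) | Rule against the PG, Wald (≥ 54/98) |
|---|---|---|
| 5% | 0.728 | 0.000 |
| 10% | 0.991 | 0.000 |
| 20% | 1.000 | 0.000 |
| 30% | 1.000 | 0.000 |
| 45% (the PG) | 1.000 | 0.028 |
| 60% (expected) | 1.000 | 0.863 |

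The 45% row gives the type I error at the PG: about 100% under the literal rule.

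If all 109 enrolled subjects were evaluable, the Wald cut-off would still be 4. The pass probabilities would be 0.800 at a true ORR of 5% and 0.996 at 10%.

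**Step 3: the rule in the protocol and the synopses, n = 98.**

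- x = 53: p = 0.5408, L = 0.4422, below 0.45.
- x = 54: p = 0.5510, L = 0.5510 − 1.960 × 0.0502 = 0.4525, above 0.45.

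At x = 54, Z = (0.5510 − 0.45)/√(0.45 × 0.55/98) = 0.1010/0.0503 = 2.010, with one-sided p = 0.0222. This matches the SAS output printed in SAP 7.2.

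The two rules are 50 responders apart: 4 of 98 against 54 of 98.

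**The case against.** The strongest reply is that nobody intends to test against zero. The first sentence of SAP 3.3 names the PG assessment. The hypotheses, the planned test, both synopses, Protocol 12.1.1.4, the SAS code and the sample size all use 45%. An analyst who runs the code in SAP 7.2 gets a test against 45%, so a device with a 10% response rate would not plausibly be declared successful. The wording may be left over from a bound on the ORR minus the PG, which would properly be compared with zero. On this view the point is an internal inconsistency and not a choice of benchmark, and the figure of about 100% describes a rule that nothing else in the plan supports.

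Most of this stands. The intent is recoverable, and the type I error figure applies only to the literal reading of SAP 3.3. The origin of the wording is an inference, because the text puts the bound on the ORR itself. The reply does not remove the need for a correction: the section headed as the success criteria states a threshold that contradicts the protocol.

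A second fair objection is that inserting the PG does not settle every detail of the cut-off. The figure of 54 of 98 holds for the normal approximation; the Clopper-Pearson bound needs 55 of 98. SAP 3.1.5 gives 52 of 98, which has a Wald lower bound of 0.432 and one-sided p = 0.054 and so fails the PG rule. These are separate matters. They do not affect the finding on SAP 3.3, but they mean a reader cannot resolve it by turning to the worked threshold in SAP 3.1.5.

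**Conclusion.** The concern holds. SAP 3.3 states the wrong threshold for the only confirmatory test in the trial. Taken as written, it passes from 4 of 98 responders with the Wald bound, or 1 of 98 with the Wilson or exact bound, and its type I error at the PG is about 100% instead of 2.5%.

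These figures assume 98 evaluable subjects and a binomial count of responders. They barely change at 109. They describe the literal rule in section 3.3 only. The trial was sized, and its test was coded, against 45%; under that rule with the normal approximation the exact type I error is 2.8% and the power at 60% is 86.3%. The error is most likely one of drafting, but it must be corrected because of where it sits.

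**What to change.** In the second sentence of SAP 3.3, replace the comparison with zero by a comparison with the PG (45%), so that it matches Protocol 12.1.1.4 and the SAP synopsis. If a difference was meant, define the bound on the observed ORR minus 45% and compare that bound with zero.

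Make the change in an amended SAP before the primary analysis, as SAP 5.12 and Protocol 12.3.6 require. A change to the success threshold after the analysis would have to be reported as a deviation and could look as if it had been chosen with the results in hand. In the same amendment it would be sensible to name the type of confidence bound and to reconcile the 52 of 98 in SAP 3.1.5 with the 54 of 98 in SAP 7.2.

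The correction to section 3.3 is one phrase. It needs no additional patients, data or analysis work.
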